# Objectives

The primary objective of this study was to assess the effect of TU-100 on postoperative quality of life in patients undergoing laparoscopic colectomy.

# Methodology

This multicenter, randomized, double-blinded, placebo-controlled study evaluated the effect of TU 100 on postoperative quality of life in patients undergoing straight, hand-assisted, or robot-assisted laparoscopic colectomy. A total daily dose of 15 g TU 100 or matching placebo (1:1) was administered for 3 days before surgery and for 28 days after surgery.

#### Number of Patients (planned and analyzed)

Approximately 68 patients were planned to be included in the study.

# Diagnosis and Main Criteria for Eligibility

#### Inclusion Criteria:

- · Were at least 18 years of age
- · Had a current diagnosis of colon cancer, diverticulitis, or benign colonic neoplasm
- · Required straight, hand-assisted, or robot-assisted laparoscopic colectomy
- · Required hospitalization for surgery and recovery

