#### Criteria for Evaluation

Primary efficacy endpoint:

- · Change in GIQLI questionnaire global score from baseline to Visit 4
- Secondary efficacy endpoints, including but not limited to, as follows:
- · Change in GIQLI global score from baseline to Visit 5
- Incidence of postoperative complication (i.e., surgical site infection, prolonged and recurrent postoperative ileus, and anastomotic leak)

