# Statistical Analysis Plan

The overall effect of TU-100 on the primary endpoint was assessed by using an analysis of covariance (ANCOVA) model with change from baseline value as the dependent variable and treatment group, baseline GIQLI global score, scheduled surgical location in the colon, and solid food before/after the first flatus as explanatory variables. The secondary endpoints were assessed by using an ANCOVA model or a Cox proportional hazards model.

The intent-to-treat (ITT) population was used for all efficacy analyses. The safety population was used for all safety analyses.

The frequencies of AEs were summarized by treatment group and by severity within treatment group. AEs were coded using the Medical Dictionary for Regulatory Activities (version 16.0). All AEs were reported.

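### Does leaving diagnosis out of the primary ANCOVA waste precision in a 68-patient trial?

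*Combined protocol and SAP*

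**What the plan says.** Inclusion Criteria admits patients who "Had a current diagnosis of colon cancer, diverticulitis, or benign colonic neoplasm". On size, the section on number of patients says "Approximately 68 patients were planned to be included in the study", and Methodology gives the allocation: "A total daily dose of 15 g TU 100 or matching placebo (1:1) was administered". The primary endpoint under Criteria for Evaluation is "Change in GIQLI questionnaire global score from baseline to Visit 4".

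The Statistical Analysis Plan section analyses that change by ANCOVA with "treatment group, baseline GIQLI global score, scheduled surgical location in the colon, and solid food before/after the first flatus as explanatory variables". Diagnosis is not in the list. Neither are centre and laparoscopic technique, although Methodology describes a multicentre trial that allows three techniques. For the population, "The intent-to-treat (ITT) population was used for all efficacy analyses".

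The document does not state a stratification factor, significance level, power, effect size, standard deviation or number of location categories. It also says nothing about how strongly diagnosis predicts GIQLI change.

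**The concern.** Cancer, an inflammatory condition and benign neoplasm are unlike reasons for the same operation. A patient whose disease causes bowel symptoms may gain from surgery, while one with few symptoms may only lose ground for a time. If so, diagnosis predicts the outcome, and leaving it out moves explainable variation into the residual. With about 34 patients per arm, diagnoses could also be unevenly split by chance.

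The omission is more noticeable because the model does spend a degree of freedom on whether solid food came before or after first flatus. That appears to be observed only after surgery, and so after dosing has begun. Replacing it with a baseline factor already in hand seems to cost almost nothing. At stake would be a wider confidence interval and lower power for the primary comparison.

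**Working it through.** **Inputs.** From the document: N = 68, 1:1 allocation (34 per arm), three diagnoses (2 df if added), and existing adjusters baseline GIQLI (1 df), location, and food/flatus (1 df). Assumed: location 1 df (2 or 3 df hardly changes the ratios), two-sided alpha 0.05, and partial R² of diagnosis from 0 to 0.20. Partial R² here means the share of the present model's residual variance that diagnosis would remove.

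**The plan's own figure.** The 68 cannot be reproduced because none of its inputs is given. As a scale for power only, 34 per arm has 80% power by normal approximation for a difference of (1.960 + 0.842) × √(2/34) = 0.68 residual SDs.

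**Adding diagnosis.** With q₀ = 3 existing non-treatment df, the variance ratio for the treatment effect is

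(1 − R²) × (N − q₀ − 3)/(N − q₀ − 5) = (1 − R²) × 62/60.

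Break-even is R² = 1 − 60/62 = 0.032.

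| Assumed partial R² | Variance ratio | CI width ratio | Power (76.9% without diagnosis) | Equivalent N |
|---|---|---|---|---|
| 0 | 1.033 | 1.017 | 75.5% | 65.8 |
| 0.03 | 1.002 | 1.002 | 76.7% | 67.8 |
| 0.05 | 0.982 | 0.991 | 77.6% | 69.3 |
| 0.10 | 0.930 | 0.965 | 79.7% | 73.1 |
| 0.20 | 0.827 | 0.910 | 84.2% | 82.3 |

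CI widths use t quantiles on 63 and 61 df; power is from the noncentral t. A simulation of 20,000 trials per R² value (assumed diagnosis mix 40/40/20) gave variance ratios of 1.032, 1.010, 0.985, 0.918 and 0.829, which agree closely.

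**What these R² values require.** Suppose each diagnosis makes up one third of patients, and one diagnosis differs from the other two by δ residual SDs at the same baseline score, location and food/flatus status. Then R² = (1/3)(2/3)δ² = 0.222δ². Break-even needs δ = √(0.032/0.222) = 0.38. R² = 0.10 needs δ = √(0.10/0.222) = 0.67, and R² = 0.20 needs δ = √(0.20/0.222) = 0.95. So the gain to about 82 patients requires a diagnosis effect larger than the 0.68 SD treatment difference used as the power scale.

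**Replacing food/flatus with diagnosis.** This is a different calculation from the table. The net cost is 1 df, but whatever the dropped term explains is lost:

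variance ratio = (62/61) × (1 − R²_diagnosis)/(1 − R²_flatus), each R² taken given baseline GIQLI and location.

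Break-even for diagnosis is 1 − (1 − R²_flatus) × 61/62. That is 1.6%, 6.5% or 11.5% if food/flatus explains an assumed 0%, 5% or 10%. With 2 location df the factor is 61/60 and the values are 1.6%, 6.6% and 11.5%. The gains in the table, and the ceiling of about 3% on the variance loss, therefore do not carry over to a replacement.

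**Chance imbalance.** Under simple randomisation with one-third prevalence, the between-arm difference in the proportion with one diagnosis has SD √(2 × 0.222/34) = 0.114. With δ = 0.67 (R² = 0.10), it adds variance 0.114² × 0.67² ≈ 0.0059 to the treatment estimate. The unadjusted variance is 4/68 = 0.0588, and 0.0059/0.0588 ≈ 10%. That is the same 10% already counted as residual variance. Imbalance is not a second loss, and the model's standard error includes it.

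**The case for a change.** The best case for adding diagnosis is asymmetry. The factor is free and fixed before randomisation. If it is useless, the variance rises by about 3%; if its partial R² is 0.10 to 0.20, the variance falls by 7% to 17%. Baseline GIQLI records where a patient starts, not how recovery proceeds, so two patients with equal baseline scores but different diagnoses may still diverge. No stratification is described, and under the one-third assumption a gap of 10 percentage points or more in one diagnosis would occur in roughly 4 trials in 10. A trial-specific imbalance of that kind is what covariate adjustment is meant to address.

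Much of this stands. Diagnosis could be prognostic, adjusting for it would be legitimate, and the arithmetic for adding it is right. What is missing is any ground for a partial R² above the break-even. The symptom argument mostly concerns preoperative burden, which baseline GIQLI measures directly. Location may absorb more. The Exclusion Criteria also narrow the mix by removing advanced or metastatic cancer, perioperative chemotherapy, Crohn's disease, ulcerative colitis, surgery during infection, obstruction or perforation, and patients needing a stoma. The asymmetry argument applies equally to centre and technique, and nothing in the document favours diagnosis over them.

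Whether food/flatus timing belongs in the model, given that treatment may influence it, is a fair question. It is a separate one, and its answer does not show that diagnosis should be included.

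**Conclusion.** The concern does not hold. It is true that diagnosis is a known three-level baseline factor and is absent from the model. That this wastes precision is not shown: it needs a partial R² above about 0.03 if diagnosis is added. If it replaces food/flatus, it needs more than about 1.6% to 11.5%, for an assumed 0% to 10% explained by that term. The document neither supports nor excludes such values. Across an assumed R² of 0 to 0.20, adding diagnosis moves the confidence interval from 1.7% wider to 9% narrower, so even the direction is open.

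In a randomised comparison, omitting a baseline factor from a linear model leaves the treatment estimate unbiased. It contradicts no figure or statement in the plan. A short covariate list is a defensible trade-off at this sample size. The conclusion rests on N = 68 analysed, equal arms, a two-sided 5% level and 1 to 3 location df. The last two are assumptions, since the document states neither.

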#### **Exclusion Criteria:**

· Had been diagnosed with rectal cancer, advanced or metastatic colon cancer, Crohn's

NCT 02232893 22 Apr 2020

disease, ulcerative colitis, or volvulus.

- · Required resection of rectal lesion
- Had received or is scheduled to receive preoperative or postoperative chemotherapy during the duration of the study
- Required emergency surgery or surgery in the presence of ongoing infection, bowel obstruction or perforated bowel
- Had any other serious condition that might adversely affect suitability for participation in this study, such as liver disorder, kidney disorders, heart failure, blood disorders, or metabolic disorders
- · Had a history of any invasive abdominal or thoracic surgery in the past 12 weeks.
- · Planned to receive any abdominal irradiation
- The patient required the formation of a stoma (ileostomy or colostomy)

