### Dose and Duration of Treatment

Patients receiving the 15 g/d dose ingested two 2.5 g sachets of TU 100 t.i.d. for 3 days preoperatively and 28 days postoperatively; patients receiving placebo followed the same dosing schedule as the patients receiving TU-100.

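### Does the stoma exclusion, which names no time point, remove patients after randomisation?

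*Combined protocol and SAP*

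**What the plan says.** The stoma item under Exclusion Criteria reads "The patient required the formation of a stoma (ileostomy or colostomy"). It carries no word that ties it to screening or to the surgical plan. The irradiation item just above it does carry one: "Planned to receive any abdominal irradiation".

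The Methodology section allocates "TU 100 or matching placebo (1:1") and says that treatment "was administered for 3 days before surgery and for 28 days after surgery". The section on dose and duration gives the same schedule: "for 3 days preoperatively and 28 days postoperatively". No randomisation date is stated, but blinded allocation must come before the first dose and therefore before the operation.

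Under Criteria for Evaluation, the primary endpoint is the GIQLI change from baseline to Visit 4. The complication endpoint covers "surgical site infection, prolonged and recurrent postoperative ileus, and anastomotic leak". On the analysis set, the Statistical Analysis Plan section states: "The intent-to-treat (ITT) population was used for all efficacy analyses". It does not define ITT further.

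**The concern.** A stoma is not always foreseen. The surgeon may decide on one during the operation, or a complication may lead to one afterwards. In this trial both would happen at least three days after the first dose. Taken literally and without a time limit, the criterion would then be met by a patient who is already randomised. The irradiation item says that it concerns what was planned and the stoma item does not, which could suggest that the omission was deliberate.

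If such patients were dropped, the loss would depend on how recovery went and possibly on treatment. The randomised comparison would no longer be intact. The patients lost would tend to have poor Visit 4 GIQLI scores, and some might have had an anastomotic leak, which the complication endpoint is meant to count. The chemotherapy item seems open to the same reading, because postoperative chemotherapy can be decided after surgery.

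**Working it through.** The plan's only relevant figure is its size: "Approximately 68 patients were planned to be included in the study". It cannot be reproduced, because no effect size, SD, alpha or power is given with it. At 1:1 it means 68/2 = 34 per arm. The main check is therefore of the text, with arithmetic only to show scale.

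**1. What the verb means in this list.** The inclusion list uses *required* for the laparoscopic operation itself and for the hospital stay. The exclusion list uses it for resection of a rectal lesion, for emergency surgery and for the stoma. The first three are needs known when the patient is considered for entry. Emergency surgery is a useful test: if *required* ran on past randomisation, a patient with an urgent reoperation would become ineligible in retrospect. That is a strained reading, and the stoma line calls for it no more than the emergency line does.

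**2. The chemotherapy item.** It already refers to treatment that is scheduled. Its other half, on chemotherapy already received, is loosely worded, since postoperative chemotherapy cannot have been received at entry. The natural pairing is received with preoperative and scheduled with postoperative. It does not show the same gap.

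**3. Whether anything removes patients.** Removal needs a rule that a randomised patient who later meets an exclusion criterion is withdrawn, replaced or left out of an analysis. The document contains none. The one statement about the efficacy analysis set is ITT for all efficacy analyses, which covers both GIQLI and complications.

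**4. Scale if patients were removed all the same.** Every rate and deficit below is assumed.

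- One patient as a share of an arm: 1/34 = 2.9%.
- Shift in an arm's mean when *k* of 34 patients, each *D* below the rest, are removed: *kD*/34. With *k* = 2 and *D* = 20 GIQLI points, 2 × 20/34 = 1.2 points. In SD units, the range runs from 1 × 1/34 = 0.03 to 3 × 2/34 = 0.18.
- Expected leaks at 3% and 5% risk: 68 × 0.03 = 2.0 and 68 × 0.05 = 3.4.
- Unplanned stomas at rate *r*: 68*r* expected, with chance of at least one 1 − (1 − *r*)^68. Power is for a two-sided 5% test at an assumed effect of 0.68 SD, where 34 per arm gives 80.1%.

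| Assumed rate | Expected patients | Chance of at least one | Power if all removed |
|---|---|---|---|
| 1% | 0.7 | 50% | 79.7% |
| 2% | 1.4 | 75% | 79.3% |
| 5% | 3.4 | 97% | 78.0% |
| 10% | 6.8 | over 99% | 75.8% |

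Loss of power would be small. Selective loss is the only real route to harm, and it depends on a removal step that the plan does not contain.

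**The case for a change.** The strongest case for a change is that ITT is left undefined. An undefined analysis set does not expressly say that a randomised patient later found to meet an exclusion criterion stays in, and some trials do use modified sets that drop such patients. No sentence says that a patient with an unplanned stoma is followed to Visits 4 and 5 or counted for complications. With about 34 per arm, one or two selective losses would be visible: at 2.0 to 3.4 expected leaks, removing one or two could take roughly a third (1/3.4 = 29%) to all of them. A clarifying sentence would cost little.

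Part of this stands. The stoma line has no time point, ITT is not defined, and an unplanned stoma would follow assignment. The rest does not carry over. ITT without a qualifier ordinarily means all randomised patients in the arm assigned, and nothing in the document points to a modified set. The leak argument needs three steps: the leak leads to a stoma, the criterion is applied after surgery, and the patient is then dropped. The first is a reasonable clinical inference that the document does not state; the second goes against the natural reading; the third has no basis in the text. The 1.2-point shift also needs both removals to fall in the same arm and none in the other, and the document gives no SD or target effect to judge it by.

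**Conclusion.** The concern does not hold as a fault in the plan. The stoma criterion is silent on timing, but read with the rest of its list it is judged at entry, and the ITT statement keeps a patient with an unplanned stoma in both the GIQLI and the complication analyses. Writing this out would record what the plan already implies; it would alter no analysis set, endpoint or estimate. Followed as written, the plan removes no patients and the shift in any arm mean is zero.

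This rests on two assumptions: that ITT has its usual meaning of all randomised patients, and that the eligibility lists apply at entry. If either failed in practice, the illustrative cost would be 2.9% of an arm per patient and up to about 0.18 SD in one arm's mean, under assumed counts and deficits that the document neither supports nor contradicts.

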### Dose and Duration of Treatment

Patients receiving the 15 g/d dose ingested two 2.5 g sachets of TU 100 t.i.d. for 3 days preoperatively and 28 days postoperatively; patients receiving placebo followed the same dosing schedule as the patients receiving TU-100.

#### Criteria for Evaluation

Primary efficacy endpoint:

- · Change in GIQLI questionnaire global score from baseline to Visit 4
- Secondary efficacy endpoints, including but not limited to, as follows:
- · Change in GIQLI global score from baseline to Visit 5
- Incidence of postoperative complication (i.e., surgical site infection, prolonged and recurrent postoperative ileus, and anastomotic leak)

# Statistical Analysis Plan

The overall effect of TU-100 on the primary endpoint was assessed by using an analysis of covariance (ANCOVA) model with change from baseline value as the dependent variable and treatment group, baseline GIQLI global score, scheduled surgical location in the colon, and solid food before/after the first flatus as explanatory variables. The secondary endpoints were assessed by using an ANCOVA model or a Cox proportional hazards model.

The intent-to-treat (ITT) population was used for all efficacy analyses. The safety population was used for all safety analyses.

The frequencies of AEs were summarized by treatment group and by severity within treatment group. AEs were coded using the Medical Dictionary for Regulatory Activities (version 16.0). All AEs were reported.

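### The only stated primary ANCOVA adjusts for the order of solid food and first flatus, which appears to be observed on treatment, so its treatment coefficient may not be the overall effect of TU-100

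*Combined protocol and SAP*

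**What the plan says.** The Objectives section sets the question: "to assess the effect of TU-100 on postoperative quality of life in patients undergoing laparoscopic colectomy". Criteria for Evaluation makes the primary endpoint "Change in GIQLI questionnaire global score from baseline to Visit 4".

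The Statistical Analysis Plan states its target and method together: "The overall effect of TU-100 on the primary endpoint was assessed by using an analysis of covariance (ANCOVA) model". Besides treatment group, the model contains "baseline GIQLI global score, scheduled surgical location in the colon, and solid food before/after the first flatus as explanatory variables". No other primary model, sensitivity analysis or mediation rationale appears.

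The text does not say whether the food/flatus term is each patient's observed sequence, a feeding policy or a stratification factor, nor when its value is fixed. The word for planned status is attached to surgical location only.

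Under Methodology, study drug "was administered for 3 days before surgery and for 28 days after surgery"; Dose and Duration of Treatment gives the same period. The secondary endpoints include a complication endpoint covering "surgical site infection, prolonged and recurrent postoperative ileus, and anastomotic leak".

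**The concern.** In a colectomy trial, first flatus is most naturally the first passage of gas after surgery. By then the patient has been randomised and has taken study drug for three days. Whether solid food came before or after it depends partly on how fast the bowel recovers. The trial itself treats bowel recovery as a possible drug effect, since postoperative ileus is part of a secondary efficacy endpoint.

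Adjusting for a variable that treatment can change raises two separate problems:

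- **Mediation.** If TU-100 changes the order and the order affects GIQLI, the adjusted coefficient leaves out the part of the effect that runs through it.
- **Shared cause.** If an unmeasured recovery factor drives both the order and GIQLI, then comparing arms within a food/flatus category compares patients who are recovering differently. This can create a difference where none exists.

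Randomisation and the ITT population protect against neither. At stake is whether the only primary estimate answers the question in the Objectives.

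**Working it through.** **Inputs from the documents.** "Approximately 68 patients were planned to be included in the study" and 1:1 allocation (Methodology) give 34 per arm if split equally. The documents give no SD, expected effect, alpha, power or food/flatus frequencies. The figure of 68 therefore cannot be reproduced, and this point does not depend on it.

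**Assumed inputs.** Residual SD 1; two-sided 5% tests; ANCOVA on treatment, baseline and a binary location, fitted without and with a binary term C for the food/flatus order. Notation: p0 and p1 are the shares with C = 1 on placebo and TU-100; g is the effect of C on GIQLI change; t is the direct treatment effect; r is the correlation between the outcome noise and a latent recovery score U, where C = 1 when U exceeds an arm-specific cut. Each scenario used 4,000 simulated trials (Monte Carlo SE of the bias about 0.004).

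**Step 1: mediation only (r = 0).** The total effect is t + g(p1 − p0), and the adjusted coefficient is t. With p0 = 0.50, p1 = 0.70, g = 0.45 and t = 0.45, the total is 0.45 + 0.45 × 0.20 = 0.54. The adjusted model estimates 0.45, a bias of −0.09.

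**Step 2: shared cause, no true effect (g = t = 0).** With φ the standard normal density at the cut, the mean of U is φ/p where C = 1 and −φ/(1 − p) where C = 0. For p0 = 0.50, p1 = 0.70:

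- C = 1: 0.497 − 0.798 = −0.301; C = 0: −1.159 + 0.798 = −0.361.
- Least squares weights these by 0.7 × 0.5/1.2 = 0.292 and 0.3 × 0.5/0.8 = 0.1875, giving −0.325.
- Multiplying by r = 0.5 gives a bias of −0.16, against −0.164 simulated.

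The same formula gives −0.05 for r = 0.3 with 50/60% (simulated −0.056) and −0.35 for r = 0.7 with 50/80% (simulated −0.345).

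**Step 3: simulated results.** Rejection means a two-sided result at 5%; a dash means not tabulated.

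| Scenario (p0/p1) | Estimate without C | Estimate with C | Rejection without C | Rejection with C |
|---|---|---|---|---|
| C unaffected (50/50), g 0.45, t 0.45 | 0.45 | 0.45 | – | – |
| C shifted (50/70), unrelated to GIQLI, null | 0.00 | 0.00 | 4.9% | 4.9% |
| Mediation (50/70), g 0.45, t 0.45 | 0.54 | 0.45 | 56% | 41% |
| Mediation (50/70), g −0.45, t 0.45 | 0.36 | 0.45 | – | – |
| Mediation (50/30), g 0.45, t 0.45 | 0.36 | 0.45 | – | – |
| Null, r 0.3 (50/60) | about 0 | −0.06 | about 5% | 5.5% |
| Null, r 0.5 (50/70) | about 0 | −0.16 | about 5% | 11% |
| Null, r 0.7 (50/80) | about 0 | −0.35 | about 5% | 33% |
| Null, r 0.5 (50/30) | about 0 | +0.17 | 2.4% for benefit | 10% for benefit |

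**Step 4: different assumptions.** With shares of 40% and 60%, g = 0.5 and t = 0.5, the estimates are 0.60 without C and 0.50 with it (power 64% and 49%). If the whole effect runs through the order (40/70%, g = 0.8, t = 0), the total is 0.8 × 0.30 = 0.24 and the adjusted estimate is 0.00.

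**The case against.** The strongest reply is that the premise is not established. The term is undefined and follows a covariate fixed before surgery. It could be a site feeding policy or a stratification factor, and then there is no problem. The text is a short synopsis, so its silence is weak evidence that no definition or sensitivity model exists. The link to bowel recovery is also indirect: ileus is listed only within a complication endpoint, the order depends on when food is offered as well as on flatus, and the study is double-blind. Where feeding is always early or always waits for flatus, TU-100 could speed flatus without changing the order. The target wording might mean only an effect pooled over covariate levels.

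The largest bias comes from one corner of the assumptions. Milder inputs give little: r = 0.3 with a 5-point shift gives about −0.02 SD, and with a 20-point shift −0.10 SD with 6.4% rejection. The standard error with 34 per arm is about √(2/34) = 0.24 SD.

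Much of this stands. Bias is a risk and has not been shown; the size is illustrative; the alternative reading is possible. It does not remove the point. Nothing in the documents fixes the variable before randomisation, and the natural reading is the observed order. A pooled reading of the target does not help either, because an effect averaged within categories that treatment has changed is still not the effect on postoperative quality of life that the Objectives ask about.

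**Conclusion.** The concern holds in conditional form and should be fixed. On the natural reading, the sole stated primary analysis conditions on a postoperative event that treatment may influence, so its coefficient cannot be assumed to be the overall effect. There is no bias if TU-100 leaves the order unchanged, or if the order is unrelated to GIQLI.

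Otherwise, the scenarios in the table give biases from about −0.35 to +0.17 residual SD. Reversing the direction of shift in the most extreme case would reverse its sign. This span covers only the scenarios tried; it is neither a bound nor a plausible interval. Every input except the 68 patients and 1:1 allocation is assumed, and the documents allow neither the size nor the direction to be determined. Confidence is medium because the meaning of the covariate is unsettled.

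**What to change.** State what the variable is and when its value is fixed.

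- **If it is the observed order:** base the primary estimate on treatment, baseline GIQLI and scheduled surgical location. Show the model with the food/flatus order as a labelled supportive analysis.
- **If results are already unblinded:** report the two models side by side and say that the change was made after unblinding.
- **If it is a feeding practice or stratification factor fixed before randomisation:** keep it, use the pre-randomisation value, and say so.

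The work is one definition and one further model. The statistical cost is lost precision if the covariate is prognostic and unaffected by treatment. In simulations with 50% in each category in both arms, dropping it changed power as follows:

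- 66% to 65% (g = 0.45, true effect 0.6 SD)
- 66% to 58% (g = 1.0, true effect 0.6 SD)
- 48% to 35% (g = 0.45 plus a shared cause with r = 0.5, true effect 0.45 SD)

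The last loss is substantial, so the definition should be settled before the model is changed.

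### Does the ITT label, with no definition or missing-data rule beside it, call for a change to the primary ANCOVA?

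*Combined protocol and SAP*

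**What the plan says.** Under Criteria for Evaluation the primary endpoint is "Change in GIQLI questionnaire global score from baseline to Visit 4". The Statistical Analysis Plan section analyses it with an "analysis of covariance (ANCOVA) model with change from baseline value as the dependent variable". The model takes treatment group, baseline score, scheduled surgical location and "solid food before/after the first flatus as explanatory variables".

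For the remaining endpoints, "The secondary endpoints were assessed by using an ANCOVA model or a Cox proportional hazards model". One of these is "Change in GIQLI global score from baseline to Visit 5". On the analysis set the section says only "The intent-to-treat (ITT) population was used for all efficacy analyses", with a parallel sentence assigning safety analyses to a safety population. Neither population is defined. The synopsis mentions no imputation, repeated-measures model, sensitivity analysis or count of missing scores. On size, "Approximately 68 patients were planned to be included in the study".

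**The concern.** A single-visit ANCOVA needs the outcome, the baseline score and every covariate for each patient. Without a rule for missing values, the software drops any patient who lacks one of them, and the result is a complete-case estimate whatever it is called.

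The design makes such gaps plausible. Dosing starts 3 days before surgery and runs for 28 days after it, so a patient can be randomised and treated and then not have the operation or not complete follow-up. If the food/flatus term is recorded as observed, it has no value for a patient who never reaches surgery. The synopsis does not say whether it is observed or set in advance.

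The stakes would be some lost precision in a trial of about 34 per arm, and bias if loss depends on post-baseline outcome differently in the two arms. The Visit 5 score looks like unused information about a missing Visit 4. The worry is confined to the ANCOVA endpoints, because a Cox model keeps patients with incomplete follow-up by censoring.

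**Working it through.** **Nothing to reproduce.** The synopsis gives no alpha, power, effect size, SD or dropout rate, so the planned 68 cannot be rebuilt. The document supplies only 68 patients and 1:1 allocation: 68/2 = 34 per arm. Every other input below is an assumption.

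**Precision.** Take two-sided alpha 0.05, 80% power and a normal approximation without covariates. The detectable standardised difference is d = (1.960 + 0.842) x sqrt(2/34) = 0.68. With a share m of patients lost, n = 34(1 - m) per arm and power = Phi(d x sqrt(n/2) - 1.960):

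| Missing | Analysed | Power at d |
|---|---|---|
| 5% | 65 | 78% |
| 10% | 61 | 76% |
| 20% | 54 | 71% |
| 30% | 48 | 65% |

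**Bias.** Simulated trials had 34 per arm, no true effect and SD 20. Correlations were 0.5 (baseline with Visit 4), 0.7 (Visit 4 with Visit 5) and 0.4 (baseline with Visit 5). All four ANCOVA terms were fitted. Loss of Visit 4 was logistic, with slope -1.2 per SD of the score driving it. Bias is in GIQLI points, TU-100 minus placebo; the last column applies if 0%, 50% or 100% of those missing Visit 4 have Visit 5. The first five rows use 10,000 trials each; the last three are separate complete-case runs with the same inputs.

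| Loss, TU-100 / placebo, and driver | Complete-case bias | In SE | Type I error | Repeated-measures bias |
|---|---|---|---|---|
| 10% / 20%, Visit 5 score | -0.92 | 0.20 | 5.7% | -0.92 / -0.35 / 0.03 |
| 10% / 20%, Visit 4 score | -1.43 | 0.32 | 6.2% | -1.43 / -1.10 / -0.89 |
| 5% / 10%, Visit 4 score | -0.76 | 0.18 | 5.2% | -0.76 / -0.61 / -0.47 |
| 10% / 30%, Visit 4 score | -2.83 | 0.61 | 9.2% | -2.83 / -2.17 / -1.79 |
| 15% / 15%, Visit 4 score, same mechanism | -0.03 | - | - | -0.03 / -0.04 / -0.03 |
| 10% / 20%, baseline score only | 0.00 | - | - | not run |
| 15% / 15%, random on TU-100, low Visit 4 on placebo | -2.36 | 0.51 | 8.3% | not run |
| 15% / 15%, opposite ends of Visit 4 by arm | -4.70 | 1.05 | 17.5% | not run |

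In the unequal-loss rows with bias, the sign reverses if the larger loss is on TU-100. As a rough check on row 1, patients missing Visit 4 score about 14 points lower there than those observed. The crude bias is then -(0.20 - 0.10) x 14 = -1.4, and baseline adjustment brings it to -0.92.

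**Scale.** With 5 model parameters and r = 0.5, the difference detectable with 80% power is 0.598 SD = 11.95 points. Rows 1 and 2 are 0.915/11.95 = 7.7% and 1.426/11.95 = 11.9% of that.

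**Shift analysis.** Suppose 3 of 34 scores are missing on TU-100 and 7 of 34 on placebo. Each 10-point shift applied to both arms moves the contrast 10 x (7 - 3)/34 = 1.18 points. The SE is 20 x sqrt(0.75) x sqrt(1/31 + 1/27) = 4.56. Moving the contrast one SE takes 4.56/(4/34) = 39 points, almost 2 SD. If the shift applies to placebo alone, it takes 4.56/(7/34) = 22 points.

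**What repeated measures buys.** With every Visit 5 present, row 1 is fully repaired but row 2 still carries -0.89. If the Visit 4 to Visit 5 correlation is 0.4, row 2 moves only from -1.41 to -1.34. The empirical SE falls from 4.64 to 4.59 in row 1 and from 4.50 to 4.41 in row 2. If Visit 5 comes after Visit 4, as the numbering suggests, patients who withdraw before Visit 4 usually lack both, and the model then changes nothing. With complete data the two models give the same Visit 4 contrast (1.317 and 1.317 in a numerical check).

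**The case for a change.** The strongest case for a change is that the gap is real and cheap to close. The section that carries the analysis plan calls the result ITT, yet a reader of this document cannot tell whom the estimate covers. Balanced dropout would not settle it: with 15% lost in each arm but for different reasons, the bias reaches half to one standard error and the type I error 8.3% to 17.5%. A definition, a rule and a table of missing Visit 4 scores by arm need no new data.

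Most of that stands as a description of the synopsis. It does not show that the analysis was complete-case. The text is plainly abridged: its list of secondary endpoints is expressly open-ended, the safety population is as undefined as the ITT one, and a section whose title promises planned and analysed numbers gives only the planned one. An omission shared by so many items points to brevity rather than to a chosen method. The large-bias cases rest on invented loss mechanisms, and nothing in the document makes them more likely than loss explained by baseline score, for which the stated model gives no bias.

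The food/flatus term raises a separate question, whether a covariate that may be measured after surgery belongs in the model. It does not bear on the missing-data method.

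**Conclusion.** No change to the plan follows. What can be verified is missing detail in a summary, of a kind that analysts have to settle before they can fit the model at all: who is in the ITT set and what is done with missing scores. That patients were dropped is an inference, and no count supports or excludes it.

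Under the same loss mechanism in both arms and 10% against 20% loss, the possible bias is 0.2 to 0.3 standard errors. It is nil when loss follows baseline alone, 0.61 standard errors at 10% against 30%, and up to about one standard error if the arms lose patients for opposite reasons. These sizes depend on the assumed SD, correlations and loss slopes; the document fixes none of them.

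A different primary model would not remove the uncertainty. Repeated measures helps only patients seen at Visit 5 but not at Visit 4, recovers almost no power, and leaves most of the bias when loss depends on Visit 4 itself. The past tense indicates that the analyses had already been carried out, so a model chosen now could only be supportive. Whether the ITT label is earned turns on the numbers analysed and the reasons for loss in each arm, which belong with the results. Similar dropout rates alone should not be read there as reassurance.
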